8.3 REPORTING OF SERIOUS ADVERSE EVENTS

All SAE reporting must include the elements described in section **8.2**.

SAE reports will be submitted to the Center for Cancer Research (CCR) at: [contact] and to the CCR PI and study coordinator. CCR SAE report form and instructions can be found at: <https://ccrod.cancer.gov/confluence/pages/viewpage.action?pageId=157942842>

Following the assessment of the SAE by OSRO, other supporting documentation of the event may be requested by the OSRO Safety and should be provided as soon as possible.

8.4 SAFETY REPORTING CRITERIA TO THE PHARMACEUTICAL COLLABORATOR

All events listed below must be reported in the defined timelines to [[contact]](mailto:[contact]).

The CCR Office of Regulatory Affairs will send all reports to the manufacturer as described below.

8.4.1 Serious Adverse Events

The Sponsor will report all serious adverse events to Celgene.

The Sponsor must inform Celgene in writing using a MEDWATCH 3500A or equivalent form of any SAE within 24 hours of being aware of the event. The written report must be completed and supplied to Celgene by facsimile or e-mail within 24 hours. The initial report must be as complete as possible, including an assessment of the causal relationship between the event and the investigational product(s). Information not available at the time of the initial report (e.g., an end date for the adverse event or laboratory values received after the report) must be documented on a follow-up report. A final report to document resolution of the SAE is required. The Celgene tracking number MRZ-CL-BRAIN-NCI-12815 and the institutional protocol number should be included on SAE reports (or on the fax cover letter) sent to Celgene. A copy of the fax transmission confirmation of the SAE report to Celgene should be attached to the SAE and retained with the patient records. For the purpose of regulatory reporting, Celgene Drug Safety will determine the expectedness of events of being related to marizomib based on the Investigator Brochure. In the United States, all suspected unexpected serious adverse reactions (SUSARs) will be reported in an expedited manner in accordance with 21 CFR 312.32.

Celgene Corporation
Global Drug Safety and Risk Management
[name]
[name]
[contact]
E-mail: [contact]
[contact]
Toll Free: [name]

8.4.2 Pregnancy

Any pregnancy occurring in either a female subject or partner of a male subject while in the treatment period, or within 28 days thereafter last dose, are considered immediately reportable events.

The Investigator will follow the female subject or partner of a male subject until completion of the pregnancy, and the Sponsor must notify Celgene Drug Safety immediately about the outcome of the pregnancy (either normal or abnormal outcome) using the CCR Pregnancy Report and Follow Up Form and CCR Pregnancy Outcome Form, Celgene Pregnancy Follow-up Report Form **Appendix D**, or approved equivalent form.

If the outcome of the pregnancy was abnormal (e.g., spontaneous or therapeutic abortion), the Investigator should report the abnormal outcome as an AE. If the abnormal outcome meets any of the serious criteria, it must be reported as an SAE to Celgene Drug Safety immediately by facsimile, or other appropriate method, within 24 hours of the Investigator's knowledge of the event using the SAE Report Form, or approved equivalent form.

All neonatal deaths that occur within 28 days of birth should be reported, without regard to causality, as SAEs. In addition, any infant death after 28 days that the Investigator suspects is related to the in utero exposure to marizomib should also be reported to Celgene Drug Safety immediately by facsimile, or other

appropriate method, within 24 hours of the Investigator's knowledge of the event using the SAE Report Form, or approved equivalent form.

8.4.3 Events of Clinical Interest (ECI): Hallucinations

Since hallucinations are an AE of interest, the type of hallucination, start and stop date, and severity are to be recorded in the CRF and a report provided to Celgene annually by the study team. See appendix [16.3](#).

8.5 REPORTING PREGNANCY

8.5.1 Maternal exposure

If a patient becomes pregnant during the course of the study, the study treatment should be discontinued immediately, and the pregnancy reported to the Sponsor no later than 24 hours of when the Investigator becomes aware of it. The Investigator should notify the Sponsor no later than 24 hours of when the outcome of the Pregnancy becomes known,

Pregnancy itself is not regarded as an SAE. However, congenital abnormalities or birth defects and spontaneous miscarriages that meet serious criteria (section [8.1.2](#)) should be reported as SAEs.

The outcome of all pregnancies (spontaneous miscarriage, elective termination, ectopic pregnancy, normal birth, or congenital abnormality) should be followed up and documented.

8.5.2 Paternal exposure

Male patients should refrain from fathering a child or donating sperm during the study and for 28 days after the last dose of marizomib.

Pregnancy of the patient's partner is not considered to be an AE. However, the outcome of all pregnancies (spontaneous miscarriage, elective termination, ectopic pregnancy, normal birth, or congenital abnormality) occurring from the date of the first dose until 28 days after the last dose should, if possible, be followed up and documented.

8.6 REGULATORY REPORTING FOR STUDIES CONDUCTED UNDER CCR-SPONSORED IND

Following notification from the investigator, CCR, the IND sponsor, will report any suspected adverse reaction that is both serious and unexpected. CCR will report an AE as a suspected adverse reaction only if there is evidence to suggest a causal relationship between the study product and the adverse event. CCR will notify FDA and all participating investigators (i.e., all investigators to whom the sponsor is providing drug under its INDs or under any investigator's IND) in an IND safety report of potential serious risks from clinical trials or any other source, as soon as possible, in accordance to 21 CFR Part 312.32.

All serious events will be reported to the FDA at least annually in a summary format.

9 CLINICAL MONITORING

As a sponsor for clinical trials, FDA regulations require the CCR to maintain a monitoring program. The CCR's program allows for confirmation of: study data, specifically data that could affect the interpretation of primary and secondary study endpoints; adherence to the protocol, regulations, ICH E6, and SOPs; and human subjects protection. This is done through independent verification of study data with source documentation focusing on:

- Informed consent process
- Eligibility confirmation
- Drug administration and accountability
- Adverse events monitoring
- Response assessment.

The monitoring program also extends to multi-site research when the CCR is the coordinating center.

This trial will be monitored by personnel employed by an CCR contractor. Monitors are qualified by training and experience to monitor the progress of clinical trials. Personnel monitoring this study will not be affiliated in any way with the trial conduct.

10 STATISTICAL CONSIDERATIONS

10.1 STATISTICAL HYPOTHESIS

The primary objective of this phase II study is to evaluate the efficacy of marizomib in *RELA*-fusion and non *RELA*-fusion ependymoma as measured by the primary endpoint of PFS6. Based on the preclinical data provided in Section 1.2.3 above, we postulate that the clinical activity of marizomib will be greatest in *RELA*-fusion supratentorial ependymoma, which has a constitutional activation of NF-κB pathway. If we see no PFS benefit with marizomib in *RELA*-fusion supratentorial ependymoma patients, then we do not expect that marizomib will benefit the non *RELA*-fusion ependymoma patients. To exploit such efficacy order of the two subgroups (*RELA*-fusion and non *RELA*-fusion), we employ a novel two-stage sequential enrichment design similar to Zang and Yuan (2016) [27]. In the first stage, we will enroll 18 patients with *RELA*-fusion ependymomas to test for clinical activity of marizomib. If 4 or more patients in Cohort 1 are progression free at 6 months, we proceed to stage 2; otherwise we terminate the trial and conclude that marizomib is not effective. Additionally, during stage 1, we will allow patients harboring *RELA*-fusion ependymoma with more extensive exposure to chemotherapy (> 2 chemotherapy regimens) to enroll. Given the preclinical data, this will enable this patient population to have access to a treatment regimen when most of the commonly used therapies have already been utilized. The responses of this group (Cohort 2) are a secondary objective and will not be used to make the determination of efficacy and will not be used for deciding to proceed to stage 2. However, the response results will be compiled as preliminary data regarding efficacy of marizomib as a salvage regimen for patients with heavily pretreated *RELA*-fusion ependymoma. At stage 2, we will enroll 16 patients with non *RELA*-fusion ependymomas (Cohort 3). Out of these 16 patients, if 9 or more patients are progression free at 6 months, we claim that marizomib is promising for treating both *RELA*-fusion and non *RELA*-fusion ependymoma; otherwise, we claim that marizomib is promising for treating *RELA*-fusion, but not for non *RELA*-fusion ependymoma. Based on historical data and clinical experience, we regard 30% of PFS6 as unpromising, and 60% of PFS6 as promising. The following table shows the operating characteristics of the above design based on 10,000 simulations.

Table 7. Operating characteristics of the two-stage sequential enrichment design

True PFS6 of RELA -fusion ependymomas	True PFS6 of	Probability of early stopping	Probability of claiming	Probability of claiming	Average sample size

	Non RELA- fusion ependymomas		effective for RELA -fusion	effective for all patients	
0.3	0.3	0.734	0.265	0.016	13.2
0.6	0.6	0.102	0.898	0.796	23.4
0.6	0.3	0.102	0.898	0.167	23.4
0.6	0.5	0.102	0.898	0.632	23.4

The study of salvage cohorts 2 and 4 is a secondary objective.

As patients in salvage cohorts 2 and 4 are highly heterogeneous, the efficacy of marizomib in *RELA*-fusion cohort 2 may not be notably higher than that in non *RELA*-fusion cohort 4. The objective of cohorts 2 and 4 is to estimate the efficacy of marizomib in recurrent ependymoma patients with multiple prior chemotherapies as measured by PFS6, PFS12, median PFS and OS. As a result, the 2-stage design will not be used for cohorts 2 and 4. Instead, we enroll patients into these cohorts simultaneously.

10.1.1 Primary Endpoint:

- Progression-free survival at 6 months of *RELA*-fusion and non *RELA*-fusion recurrent ependymoma patients treated with marizomib (Cohorts 1-4) will be assessed as proportion of patients that are progression-free at 6 months timepoint after initiation of treatment.

10.1.2 Secondary Endpoint(s):

- Progression-free survival at 12 months of *RELA*-fusion and non *RELA*-fusion recurrent ependymoma patients treated with marizomib (Cohorts 1-4) will be assessed as proportion of patients that are progression-free at 12 months timepoint after initiation of treatment
- Median progression-free survival (PFS) of *RELA*-fusion and non *RELA*-fusion recurrent ependymoma patients treated with marizomib (Cohorts 1-4) will be assessed as median amount of time subject survives without disease progression after initiation of treatment
- Overall survival (OS) of *RELA*-fusion and non *RELA*-fusion recurrent ependymoma patients treated with marizomib (Cohorts 1-4) will be assessed as median amount of time subject survives after initiation of therapy
- Progression-free survival at 6 months of *RELA*-fusion and non *RELA*-fusion recurrent ependymoma patients with with more than 2 prior chemotherapies treated with marizomib (Cohorts 2 and 4) will be assessed as proportion of patients that are progression-free at 6 months timepoint after initiation of treatment.
- Progression-free survival at 12 months of *RELA*-fusion and non *RELA*-fusion recurrent ependymoma patients with with more than 2 prior chemotherapies treated with marizomib (Cohorts 2 and 4) will be assessed as proportion of patients that are progression-free at 12 months timepoint after initiation of treatment
- Median progression-free survival (PFS) of *RELA*-fusion and non *RELA*-fusion recurrent ependymoma patients with with more than 2 prior chemotherapies treated with marizomib (Cohorts 2 and 4) will be assessed as median amount of time subject survives after initiation of therapy

- Overall survival (OS) of *RELA*-fusion and non *RELA*-fusion recurrent ependymoma patients with with more than 2 prior chemotherapies treated with marizomib (Cohorts 2 and 4) will be assessed as median amount of time subject survives after initiation of therapy
- Objective response to marizomib in *RELA*-fusion and non *RELA*-fusion recurrent ependymoma patients with with more than 2 prior chemotherapies treated with marizomib (Cohorts 2 and 4) will be assessed using RANO Criteria for Response **6.3.3**.
- Safety of marizomib in recurrent ependymoma patients and in a subset of patients with more than 2 prior chemotherapies (Cohorts 2 and 4) will be scored using CTCAE version 5.0.
- Outcome measures using self-reported symptom severity and interference with daily activities using the MDASI-BT and/or MDASI-SP instrument.

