10.2 SAMPLE SIZE DETERMINATION

To meet objectives of this study we need 50 patients. Considering screen failures, the total number of patients is set at 70 patients.

The sample size is calibrated and determined based on simulation to obtain desirable operating characteristics, as shown in **Table 7**. For example, when the treatment is effective (i.e., PFS6=0.6) for both *RELA*-fusion and Non *RELA*-fusion ependymomas, we have 0.796 chance to conclude that the treatment is effective for both types of ependymomas, and when the treatment is not effective (i.e., PFS6=0.3) for both *RELA*-fusion and Non *RELA*-fusion ependymomas, the probability of incorrectly claiming that the treatment effective is 0.016. Given the sample size of 9 (cohort 1), the 95% confidence interval of PFS6 is not wider than 0.32 on each side. Given the sample size of 16 (Stage 2 cohort 3), the 95% confidence interval of PFS6 and PFS12 is not wider than 0.24 on each side. The two salvage cohorts 2 and 4 are secondary and will not contribute to the statistical power of the study.

The anticipated accrual rate is 1 patient per month for *RELA*-fusion ependymoma cohorts and 1-2 patients per month for the non *RELA*-fusion ependymoma cohorts.

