10.4.4 Planned Interim Analyses

Two-stage sequential enrichment design will be used for this trial. In the first stage, we will enroll 9 patients with *RELA*-fusion ependymomas (Cohort 1) to test for clinical activity of marizomib. If 4 or more patients are progression free at 6 months, we proceed to stage 2; otherwise we terminate the trial and conclude that marizomib is not effective. At stage 2, we will enroll 32 patients with non *RELA*-fusion ependymomas (Cohort 3 and 4). From Cohort 3, if 9 or more of 16 patients are progression free at 6 months, we claim that marizomib is promising for treating both *RELA*-fusion and non *RELA*-fusion ependymoma; otherwise, we claim that marizomib is promising for treating *RELA*-fusion, but not for non *RELA*-fusion ependymoma. As above, PFS-6 for Cohort 4 will also be measured in patients with non-*RELA* fusion ependymoma that has been extensively treated. These data will be compiled as preliminary data regarding efficacy of marizomib as a salvage regimen for patients with heavily pretreated non-*RELA*-fusion ependymoma.

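### Eight or fewer successes of 16 in Cohort 3 is written up as a negative for non RELA-fusion and a contrast with RELA-fusion, which the decision rule cannot support

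*Combined protocol and SAP*

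**What the plan says.** Section 10.1 sets the benchmarks: "we regard 30% of PFS6 as unpromising, and 60% of PFS6 as promising".

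The stage 1 decision uses Cohort 1 only. Section 10.4.4: "In the first stage, we will enroll 9 patients with *RELA*-fusion ependymomas (Cohort 1) to test for clinical activity of marizomib". Section 10.1: "If 4 or more patients in Cohort 1 are progression free at 6 months, we proceed to stage 2".

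The stage 2 decision uses Cohort 3 only. Section 10.1: "Out of these 16 patients, if 9 or more patients are progression free at 6 months, we claim that marizomib is promising for treating both" types. Section 10.4.4 repeats the cut-off: "From Cohort 3, if 9 or more of 16 patients are progression free at 6 months".

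For any lower Cohort 3 count, both sections give the same conclusion: "otherwise, we claim that marizomib is promising for treating *RELA*-fusion, but not for non *RELA*-fusion ependymoma". There is no third outcome.

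Section 10.4.1 plans Kaplan-Meier PFS6 with 95% confidence intervals, and a log-rank test and proportional hazards model comparing the two types. Neither is tied to the claim. Section 10.2 takes its power from Table 7: "we have 0.796 chance to conclude that the treatment is effective for both types of ependymomas" when both true rates are 0.6. Table 7 has no column for the RELA-only claim.

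**The concern.** The RELA-only conclusion has two parts that the data need not support. One is a negative for non RELA-fusion, reached only because a count fell below a threshold. The other is a contrast between types, reached because one cohort passed its hurdle and the other missed a stricter one.

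This is one of only two endings open to the trial once stage 2 begins, and it would steer further development towards one molecular type. Section 5.1 says the study will help show whether RELA fusion is a predictive biomarker, so the sentence is likely to be read as evidence on that question. If it often appears when the drug is equally active in both types, it would mislead.

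**Working it through.** **Inputs.** Cohort 1: n = 9, pass at 4 or more. Cohort 3: n = 16, pass at 9 or more. Benchmarks: 0.30 and 0.60 (all 10.1 and 10.4.4). Table 7 rests on 10,000 simulations. X1 and X2 are the success counts in Cohorts 1 and 3, treated as independent binomials with every patient's 6-month status known.

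**Step 1: reproduce Table 7, stage 1.** P(X1 ≥ 4 | 9, 0.30) = 0.270 (printed 0.265). P(X1 ≥ 4 | 9, 0.60) = 0.901 (printed 0.898). Average sample size is 9 + 16 × P(pass): 13.3 and 23.4 (printed 13.2 and 23.4). Stage 1 reproduces.

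**Step 2: reproduce Table 7, claim for all patients.** The written rule gives P(X1 ≥ 4) × P(X2 ≥ 9).

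| True PFS6, RELA / non RELA | Printed | Written rule, exact | Pooled rule: X1 ≥ 4 and X1 + X2 ≥ 13 of 25 |
|---|---|---|---|
| 0.3 / 0.3 | 0.016 | 0.007 | 0.015 |
| 0.6 / 0.6 | 0.796 | 0.645 | 0.799 |
| 0.6 / 0.3 | 0.167 | 0.023 | 0.163 |
| 0.6 / 0.5 | 0.632 | 0.362 | 0.623 |

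The simulation standard error is about √(0.645 × 0.355 / 10,000) = 0.005, so the differences from the written rule are not simulation noise. The pooled rule fits every row to within 0.01, but it is written nowhere in the plan.

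**Step 3: hurdles.** At a true 0.30, P(X1 ≥ 4 | 9) = 0.270 and P(X2 ≥ 9 | 16) = 0.026. At a true 0.60, the pass probabilities are 0.9006 and 0.7161, so Cohort 3 misses with probability 0.2839.

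**Step 4: probability of the RELA-only claim.** Under the written rule this is P(X1 ≥ 4) × P(X2 ≤ 8).
- Both 0.60: 0.9006 × 0.2839 = 0.256.
- Both 0.50: 0.7461 × 0.5982 = 0.446.
- Both 0.70: 0.9747 × 0.0744 = 0.072.
- Both 0.30: 0.2703 × 0.9743 = 0.263.

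For both at 0.60, Table 7 as printed implies 0.898 − 0.796 = 0.102. The pooled rule gives 0.101.

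**Step 5: what a miss excludes.** Exact (Clopper-Pearson) 95% upper limits for Cohort 3 are 0.587 for 5 of 16, 0.646 for 6, 0.701 for 7 and 0.753 for 8. With 6 to 8 successes, 0.60 is not excluded.

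**Step 6: reversal.** With 4 of 9 (44.4%) and 8 of 16 (50.0%), the type with the higher rate is the one rejected. The one-sided exact p-values against 0.30 are 0.270 and 0.074. With both true rates at 0.60, this outcome has probability 0.1672 × 0.1417 = 0.024. It is the only reversal by observed rate.

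**Step 7: can these cohorts show a difference?** With 8 of 16 in Cohort 3, a two-sided Fisher test gives p < 0.05 only if Cohort 1 has 9 of 9 (p = 0.022). Over all RELA-only outcomes, the share with Fisher p < 0.05 and the higher rate in RELA-fusion is 0.0148 / 0.2557 = 6% when both rates are 0.60, and 0.2448 / 0.8775 = 28% when they are 0.60 and 0.30.

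**The case against.** **Table 7 gives 10.2%, not 25.6%.** The sponsor could cite the printed figure. It does not follow from the 9-of-16 rule stated in two sections, but the documents do not show which rule was intended. The 25.6% therefore holds for the written rule with both true rates at 0.60, and must be labelled so.

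**The word used is promising.** This is a phase II screening label. The clause can be read as two separate go/no-go decisions, and neither section states that the effect differs by RELA status. A reader might infer that the plan would declare the drug to work only in RELA-fusion tumours; the text does not go that far. Even so, putting the two verdicts in one sentence invites the contrast, and nothing in the plan warns against it.

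**The efficacy order justifies the sequence.** Section 10.1 postulates, on preclinical grounds, that activity will be greatest in RELA-fusion tumours. That supports testing them first. It does not make a Cohort 3 miss evidence of inactivity, and sections 1.2.3 and 1.2.5 give reasons why non RELA-fusion tumours might also respond.

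**Intervals and a comparison are already planned.** This is correct (10.4.1). What is missing is any link between them and the claim.

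**A two-outcome rule is legitimate in phase II.** Agreed. Calling 6 to 8 of 16 inconclusive because the interval contains 0.60 also applies that standard to one side only: 9 of 16 has an exact 95% interval of 0.299 to 0.802, which contains 0.30, yet counts as promising. A formal inconclusive band is a design preference.

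**Conclusion.** The concern holds for the wording of a prespecified primary conclusion. Under the rule as written, any Cohort 3 count from 0 to 8 yields a negative for non RELA-fusion and an implied contrast, although no comparison enters the rule and the hurdles have type I errors of 0.270 and 0.026. If both types truly have PFS6 of 0.60, this happens in 25.6% of trials, assuming independent binomial counts and complete 6-month status. The figure depends on the true rate (44.6% with both at 0.50, 7.2% with both at 0.70) and on the rule: it would be about 10% if the pooled rule that fits Table 7 was intended.

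Two stronger readings are not supported. The reversal at 4 of 9 with 8 of 16 is possible but uncommon, at 2.4% of trials with both rates at 0.60, so the rule does not routinely reject the type with the higher rate. Nor is the 9-of-16 success criterion itself shown to be wrong; the fault lies in what is concluded from missing it.

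**What to change.** 1. First reconcile Table 7 and the power in 10.2 with the decision rule. If 9 of 16 in Cohort 3 stands, the claim-for-all column needs recomputing (0.645, not 0.796, with both rates at 0.60). If a pooled rule was intended, 10.1 and 10.4.4 must say so, and the figures above change.
2. Keep the 9-of-16 success rule. In 10.1 and 10.4.4 replace the clause for a Cohort 3 miss with: *marizomib is promising for RELA-fusion; promising activity in non RELA-fusion ependymoma was not shown*. Add that this is not evidence that the effect differs by RELA status.
3. State that the conclusion is interpreted alongside each cohort's PFS6 with its exact 95% confidence interval and the between-type comparison already in 10.4.1, noting when the Cohort 3 interval still includes 0.60.
4. Add a column to Table 7 for the probability of the RELA-only claim.

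The cost is wording in two sections and a recomputed table; no patients are added. The downside is that a Cohort 3 miss no longer gives a firm negative for non RELA-fusion.

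A formal split into 0–5 (not promising) and 6–8 (inconclusive) is optional. It would cut the not-promising verdict at a true 0.60 from 28.4% to 1.9% of stage 2 results, but would label 31% of them inconclusive at a true 0.30 and 49% at a true 0.50.
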